6.5.2 Vital signs

Body temperature and respiratory rate will be measured at Screening, at 6, 12, 24 and 48 hours after start of study drug infusion in serelaxin arm and daily through index hospitalization, at Day 5, at discharge, and then at Day 14. Patients discharged prior to Day 5 will return to the hospital/clinic for Day 5 procedures. For the SOC patients, body temperature and respiratory rate will be measured at Screening, at 6, 12, 24 and 48 hours after randomization and daily through index hospitalization, at Day 5, at discharge, and then at Day 14, according to the scheduled visits.

Daily measurements may be made and recorded by trained study personnel as well as trained healthcare personnel as part of their routine clinical duties.

BP and HR measurements should be performed for all patients at the beginning of the screening period (after ICF signature) and at the end of the screening period (prior to randomization).

For serelaxin patients, BP and heart rate (HR) measurements will be also performed before the immediate start of study drug administration (0 hours pre infusion start), throughout study drug infusion at 30 and 60 minutes, then every hour for the first 6 hours, and then every 3 hours, including night time hours. Post-infusion BP and HR are to be measured every 3 hours until 12 hours following end of infusion, then every 6 hours for 48 hours and then every 24

hours through index hospitalization, at Day 5, at discharge, and then at Day 14. For patients randomized to the SOC group, BP and HR measurements should be also performed at 6, 12, 24, 48 hours, including night time hours, daily through index hospitalization, at Day 5, at discharge, and then at Day 14.

All measurements should be performed as close as possible to specified timepoint.

BP and HR are to be measured with the patient in the same position and with the same equipment using the same arm throughout study drug infusion. These measurements may be made and recorded by trained healthcare personnel as part of their routine clinical duties, as well as trained study personnel.

If at any time during dosing, the subject's systolic blood pressure decreases by >40 mmHg from the systolic blood pressure measured just before the start of study drug infusion but is \geq 100 mmHg in two consecutive measurements 15 min apart, serelaxin infusion rate will be decreased by 50% for the remainder of the 48 hour study drug administration. Serelaxin administration will be permanently discontinued at any time if in two consecutive measurements 15 minutes apart, systolic blood pressure is reduced to <100 mmHg (also see details in [Section 5.5.5](#)).

Should the study drug dose be decreased or the study drug be discontinued prematurely due to blood pressure decrease, measurements should be taken every half hour through 2 hours following the blood pressure decrease event, and then hourly through 5 hours after event onset. Upon completion of the 5-hour post event onset time point, heart rate and blood pressure measurements should be resumed as outlined above.

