Safety risks and events of interest through Day 5 and Day 14 will be summarized by treatment group and tabulated by safety risk / events of interest, NMQ, HLGT, SMQ or SOC, and Preferred Term of MedDRA dictionary. Absolute and relative frequency of patients who have experienced each type of event will be presented.

	Statistical Analysis Plan
	Sponsor: NOVARTIS
	Protocol number: CRLX030A3301

Table 5.3-1: MedDRA* search specifications to evaluate safety risks

Safety Risk	Specification
Hypotension (identified)	NMQ 'Hypotension' (Broad) CMQ ' Hemoglobin/ hematocrit transient decrease '
Hemoglobin/ hematocrit transient decrease (potential)	
 • SMQ 'Haemorrhages' (Broad) • HLGT 'Anaemias nonhaemolytic and marrow depression' • SMQ 'Haematopoietic erythropenia' (Broad)
Fetotoxicity and teratogenicity (potential)	SMQ 'Pregnancy and neonatal topics' (Broad)

CMQ: Customized MedDRA query; HLGT: High level group term; NMQ: Novartis MedDRA query; SMQ: Standardized MedDRA query.

* According to MedDRA v19.1. Specifications could possibly change before database lock.

	Statistical Analysis Plan
	Sponsor: NOVARTIS
	Protocol number: CRLX030A3301

Table 5.3-2: MedDRA* search specifications to evaluate events of interest

Event of Interest	Specification
Menorrhagia/Metrorrhagia	HLGT 'Menstrual cycle and uterine bleeding disorders'
Hypokalemia	NMQ 'Hypokalemia' (Broad)
Hypersensitivity/Immunogenicity	CMQ ' Hypersensitivity, Immunogenicity, Cutaneous reactions ': 
 • SMQ 'Hypersensitivity' (Broad) • SMQ 'Angioedema' (Broad) • SMQ 'Anaphylactic reaction' (Broad) • SOC 'Immune system disorders' • HLGT 'Immunology and allergy investigations' • HLGT 'Administration site reactions' • SMQ 'Severe cutaneous adverse reactions' (Broad)
Cardiac failure	SMQ 'Cardiac failure' (Broad) CMQ ' Cardiac arrhythmias/QT prolongation ': 
 • SMQ 'Torsade de pointes/QT prolongation' (Broad) • SMQ 'Cardiac arrhythmias' (Broad)
QT prolongation	
Thromboembolic events	SMQ 'Emolic and thrombotic events' (Broad) CMQ ' Renal impairment ': 
 • SMQ 'Acute renal failure' (Broad) • PT 'Chronic kidney disease'
Renal impairment	
Respiratory failure	SMQ 'Respiratory failure' (Broad)
Hepatotoxicity	SMQ 'Drug related hepatic disorders – comprehensive search' (Broad)
Potential promotion of cancers	SMQ 'Malignancies' (Broad)

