For the serelaxin arm only, the number and proportion of patients who experienced a confirmed systolic blood pressure decrease event during study drug administration will be provided. Percentages will be computed considering patients in the analysis population.

The number and proportion of patients who experienced 0, 1, 2, >2 confirmed systolic blood pressure decrease events will be provided together with the number and proportion of patients who experienced asymptomatic/symptomatic events (as recorded on the "Systolic Blood pressure Decrease Event" eCRF page).

The total number of events will be further characterized, showing absolute and relative frequencies of events for the following characteristics:

- Outcome: not recovered/not resolved, recovered/resolved, recovering/resolving, recovered/resolved with sequelae, fatal, unknown
- Action taken with study treatment: none, dose adjusted but not discontinued, permanently discontinued, dose adjusted then permanently discontinued

The category of "dose adjusted then permanently discontinued" for action taken is derived by combining the categories "dose adjusted but not discontinued" and "permanently discontinued" when recorded separately in the eCRF for the same CBPDE.

- Medications or therapies taken: yes or no, if yes type of medication/therapy (fluids/crystalloids, inotropes, vasoressors, circulatory support, mechanical ventilation, other)

Percentages will be computed considering events with non-missing information.

The number and proportion of patients who experienced at least one confirmed systolic blood pressure decrease events will be also presented by outcome, action taken and medications/therapies taken.

The number and proportion of patients who experienced at least one systolic blood pressure decrease events will be also presented by type of event in terms of SBP onset value (mmHg):

- if systolic blood pressure decreased by > 40 mmHg from baseline but was ≥ 100 mmHg;
- if systolic blood pressure reduced to < 100 mmHg.

	<h2 style="margin: 0;">Statistical Analysis Plan</h2>
	Sponsor: NOVARTIS Protocol number: CRLX030A3301

The SBP value (mmHg) at baseline (i.e., at randomization) will be summarized for patients with a confirmed SBP decrease event and for those without a confirmed SBP decrease event.

The following summaries will be presented for patients with a confirmed SBP decrease event:

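### The only between-arm comparison of hypotension events rests on open-label AE reports, with 21 scheduled BP readings on serelaxin against 4 on SOC in the first 48 h

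*Protocol*

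**What the plan says.** Protocol 6.5 assesses safety by comparing serelaxin with SOC on AE frequency and vital-sign changes, among other things. SAP Table 5.3-1 lists three safety risks. Hypotension is marked as identified and the other two as potential. The SAP adds: "Safety risks and events of interest through Day 5 and Day 14 will be summarized by treatment group".

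The BP schedules in Protocol 6.5.2 differ by arm:
- Serelaxin, during infusion: "throughout study drug infusion at 30 and 60 minutes, then every hour for the first 6 hours, and then every 3 hours".
- SOC: "For patients randomized to the SOC group, BP and HR measurements should be also performed at 6, 12, 24, 48 hours".
- Serelaxin, afterwards: "Post-infusion BP and HR are to be measured every 3 hours until 12 hours following end of infusion, then every 6 hours".
- After a BP decrease that led to a lower dose or to stopping: "measurements should be taken every half hour through 2 hours following the blood pressure decrease event", then hourly to 5 h. This applies to study drug only.

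Measured BP is used in two ways:
- SAP 5.3, on systolic BP decrease events: "For the serelaxin arm only, the number and proportion of patients who experienced a confirmed systolic blood pressure decrease event" is reported. There is no SOC counterpart.
- Protocol 9.5.2 compares vital-sign changes between arms by t-test at time points that both arms share. SAP 5.3 (Vital signs) gives the between-arm difference in absolute change with a 95% CI, the median, quartiles and range by arm, and line plots of mean SBP and DBP.

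Protocol 5.4 leaves treatment open to patients, site staff and assessors. Neither document plans a both-arm proportion of patients below an SBP threshold.

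**The concern.** A hypotension AE exists only if someone measures or notices low pressure and then decides that it is reportable. Both steps are more likely on serelaxin. Pressure is read more often. A confirmed fall requires a dosing action and has its own eCRF page, and the AE form asks whether the AE meets the definition of such an event. That definition is tied to the infusion, so SOC has no matching prompt. The people reporting also know the arm.

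The by-arm hypotension table therefore mixes any drug effect with closer observation. The between-arm vital-sign analysis does not separate the two, because a difference in mean change does not say how many patients fell low. The gap is noticeable because the SAP does plan both-arm threshold tables for laboratory values, liver tests and ECG parameters including heart rate (Tables 5.3-3 to 5.3-6), but none for SBP.

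**Working it through.** The plan states no figure for this point, so there is none to reproduce.

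**1. Scheduled readings (Protocol 6.5.2).**
- Serelaxin to 48 h: 0.5, 1, 2, 3, 4, 5, 6 h (7), then 9 to 48 h in 3-h steps (14). 7 + 14 = **21**, or 22 with the pre-infusion reading.
- SOC to 48 h: 6, 12, 24, 48 h = **4**.
- By 6 h the counts are 7 and 1; by 24 h, 13 and 3.
- To 120 h for a patient still in hospital: serelaxin 21 + 4 (51 to 60 h) + 8 (66 to 108 h) + 1 = 34; SOC 4 + 3 daily = 7.
- An event that changes dosing adds 4 half-hourly and 3 hourly readings = 7, on serelaxin only.

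**2. What each planned output can show.**

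| Output | Both arms? | Counts patients who fell low? | Unaffected by the extra readings? |
|---|---|---|---|
| MedDRA hypotension query on AEs | yes | yes, as reported | no |
| Confirmed BP decrease events | serelaxin only | yes | not applicable |
| Change in SBP/DBP at common times | yes | no | yes |

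No output has all three properties.

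**3. How far the schedules alone could separate the arms (illustration).** Assume one episode of duration d with onset uniform over 0 to 48 h, found only if a scheduled reading falls within it. Then P(found) = sum over gaps between readings of min(gap, d) / 48.
- Serelaxin gaps: two of 0.5 h, five of 1 h, fourteen of 3 h. SOC gaps: 6, 6, 12, 24 h.
- d = 1 h: (1 + 5 + 14)/48 = 0.417 v 4/48 = 0.083; ratio 5.0.
- d = 3 h: 48/48 = 1.0 v 12/48 = 0.25; ratio 4.0.
- d = 6 h: 1.0 v 24/48 = 0.50; ratio 2.0.
- d = 12 h: 1.0 v (6 + 6 + 12 + 12)/48 = 0.75; ratio 1.33.

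**4. Allowing for routine care.** Let a share b of episodes be found anyway in both arms. Observed risk = true risk × [b + (1 − b) × P(found)]. Take a true risk of 10% in both arms, d = 3 h, and 3183 patients randomized 2:1 (2122 and 1061). The last column supposes a two-sided test at 0.05, which the plan does not specify for this table.

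| b | Serelaxin | SOC | Ratio | Chance of a nominally significant difference |
|---|---|---|---|---|
| 0 | 10.0% | 2.5% | 4.0 | about 100% |
| 0.5 | 10.0% | 6.3% | 1.6 | 95% |
| 0.8 | 10.0% | 8.5% | 1.18 | 27% |

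With 1-h episodes the ratios are 5.0, 1.31 and 1.08. Episode duration, true risk and b are assumptions; the documents give none of them.

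**5. Single low readings.** A simulation used the same autocorrelated SBP process in both arms (assumed mean 125 to 130, between-patient SD 13 to 14, within-patient SD 8 to 10 mmHg, autocorrelation time 3 to 6 h). At least one reading below 100 mmHg was seen in 11 to 27% on the serelaxin schedule and 6 to 16% on the SOC schedule, a ratio of 1.7 to 2.1. This concerns single readings, not reported AEs.

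**6. After restriction to shared times.** With 6, 12, 24 and 48 h only, each arm has 4 scheduled readings and the detection ratio in step 3 becomes 1.0.

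**The case against.** Four arguments carry weight.

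- *BP is already compared fairly.* The common-time-point analysis does not use the extra readings, and its minimum and quartiles show part of the lower tail. This stands, and a reader who inferred that BP is not compared between arms at all would be wrong. It still yields no proportion of patients who fell low.
- *A low reading is not an AE.* Under Protocol 7.1 an abnormal result counts only if it causes signs or symptoms, is clinically significant or needs therapy. Symptomatic or serious hypotension depends less on scheduled readings, and Protocol 5.5.5 expects continuous cardiac monitoring in many centers, although it says so in discussing screening. So the ratios above do not estimate the bias in the AE table. A reader might infer that the table would show an excess even for an inert infusion, or that the trial cannot answer its tolerability question. The documents support neither.
- *Serelaxin-only event counts are legitimate.* The confirmed event is defined against pre-infusion SBP with a 15-minute confirmation, so SOC has no equivalent. This stands; the flaw is the missing both-arm measure, not that table.
- *Shared readings can hide harm.* They drop six of the seven serelaxin readings in the first 6 h. By then an early fall may already have led to a reduced or stopped infusion, or to corrective measures. This also stands. It might be inferred that the AE table should be set aside in favour of the new one, but that would exchange a bias against the drug for one that can conceal its effect.

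**Conclusion.** The point holds as one missing analysis. The by-arm hypotension AE table is open to detection bias towards more hypotension on serelaxin, because of 21 against 4 scheduled readings in 48 h, prompts that exist only on study drug, and open-label reporting. The counts follow directly from Protocol 6.5.2. The size of the bias is unknown: the illustrative ratios run from 5.0 down to 1.08, depending on assumed episode length and on how much routine care finds. The direction is the same in every scenario calculated. The sponsor should act, because hypotension is the identified risk and a more even comparison can be made from existing data.

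**What to change.** In SAP 5.3 add one both-arm table on the Safety set with two proportions: patients with any SBP below 100 mmHg, and patients with a fall of more than 40 mmHg from end-of-screening SBP, which is measured in both arms. Use only the shared nominal readings (6, 12, 24 and 48 h, then daily to Day 5). Give the risk difference with a 95% CI and the number of patients with a reading at each time. Both cut-offs are already the SAP's own, although its 40 mmHg fall is measured from the pre-infusion value.

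Place this table beside the MedDRA hypotension table, footnote the latter to say that monitoring intensity differed by arm, and interpret the two together.

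The cost is one table and one footnote, with no change to visits, dosing rules or data collection. The SAP should state three limits of the new table:
- It misses falls between shared readings, notably in the first 6 h.
- It can understate a true drug effect where the infusion was already reduced or stopped, or corrective measures were taken.
- Its times are nominal, counted from infusion start on serelaxin and from randomization on SOC.

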6.5.3 Height and weight

Height in centimeters (cm) or inches (inch) will be measured at screening only.

Body weight (to the nearest 0.1 kilogram [kg] or 0.1 pounds [lbs] in indoor clothing, but without shoes) will be measured at Screening and at 24 and 48 hours after study drug infusion in serelaxin arm, and daily through index hospitalization, at discharge, and at Day 5 and then at Day 14. For the SOC patients, body weight will be measured at screening, 24 and 48 hours after randomization and daily through index hospitalization, at discharge, and at Day 5, and then at Day 14. These measurements during hospitalization can be performed at any time of the day.

If patient's body height/weight cannot be measured at Screening because of the patient's physical condition, verbal height/weight will be acceptable. Height/weight measurements shall be obtained as soon as the patient is physically able.

6.5.4 Laboratory evaluations

All screening, baseline and post-baseline specimens [REDACTED]

[REDACTED] will be analyzed by the local laboratory.

Following randomization, local laboratory collections can be adjusted to conform to the hospital's routine laboratory collection schedule and can be collected at any time of day.

[REDACTED]

[REDACTED]

Laboratory values that exceed the boundaries of a notable laboratory abnormality should be assessed for AEs and additional evaluations should be performed, as judged appropriate by the investigator. If the laboratory abnormality induces clinical signs and symptoms or requires therapeutic intervention, then the diagnosis or medical condition must be entered on the AE screen of the patient's eCRF. If the laboratory abnormality is the primary reason for an unforeseen hospitalization or otherwise fulfills the seriousness category of an AE, then the procedure for immediate notification of SAEs must be followed. Likewise, if the laboratory abnormality leads to discontinuation from the study, then the patient must be followed until the abnormality resolves or is judged to be permanent.

Clinical laboratory tests including hematology and chemistry will be performed locally at screening, at 24 and 48 hours, at Day 5, at discharge and then Day 14 (in both arms). The tests done at each visit are standard medical tests. A total of approximately 10 mL will be collected when each blood sample is taken.

Urinalysis will be conducted at baseline, 24 and 48 hours only and analyzed locally.

In those sites in which markers of cardiac injury or stress are measured as per local practice the values should be entered into the eCRF ONLY in the context of a WHF event.

6.5.4.1 Hematology

Clinical hematology evaluations will include measurement of hemoglobin, hematocrit, red blood cell count, white blood cell count, differential cell count (monocytes, neutrophils, eosinophils, lymphocytes, basophils), and platelet count.

6.5.4.2 Clinical chemistry

Serum chemistry evaluations will include measurement of blood urea nitrogen (BUN) or urea, serum creatinine, total bilirubin, phosphate, ALT, AST, alkaline phosphatase, sodium, potassium, calcium, total cholesterol, triglycerides, LDL, HDL, glucose, uric acid, albumin and total protein. In addition, hemoglobinA1c will be measured at screening only. For Liver Events only, fractionated bilirubin, which includes testing for total bilirubin, direct bilirubin, and indirect bilirubin, should be performed in accordance with [Table 14-2](#).

6.5.4.3 Urinalysis

Urinalysis will include measurement of glucose, ketones, pH, protein and specific gravity. The analysis will be performed according to local lab methods /procedures.

6.5.5 Electrocardiogram (ECG)

ECGs will be performed and interpreted locally at screening and at Day 5 and at discharge. The ECG interpretation and the person interpreting the ECG must be recorded in the source documents.

ECGs must be recorded after 10 minutes rest in the supine position to ensure a stable baseline. The preferred sequence of cardiovascular data collection during study visits is ECG collection first, followed by vital signs, and blood sampling. The Fridericia QT correction formula (QTcF) should be used for clinical decisions.

Single 12 lead ECGs are collected. The original ECGs on non-heat-sensitive paper or a certified copy on non-heat sensitive paper, appropriately signed, should be collected and archived at the study site.

Each ECG tracing should be labeled with study number, subject initials, subject number, date and time, and filed in the study site source documents. For any ECGs with subject safety concerns, two additional ECGs should be performed to confirm the safety finding. Clinically significant ECG findings prior to dosing with investigational treatment must be discussed with the sponsor.

Clinically significant abnormalities should be recorded on the relevant section of the medical history/Current medical conditions/AE eCRF page as appropriate.

6.5.6 Appropriateness of safety measurements

The safety assessments selected are standard for this indication/patient population.

6.6.5 Resource utilization

Analyses will be undertaken, as appropriate, to assess the effects of treatments on healthcare resource utilization (RU) parameters.

Throughout the index hospitalization, the level of healthcare resource utilization shall be assessed by the overall length of stay, length of time in specific inpatient care units and procedures rendered during hospital stay.

Data for a health economic analysis will be collected from eCRFs, most notably Hospital Discharge, Re-hospitalization and Death. Data on medical resource use will be collected for all enrolled patients from the index hospitalization at discharge and at Day 5, and then at Day 14 and through phone contact at Day 30.

The endpoints and methods of the health economic analysis will be detailed separately in the statistical analysis plan.

6.6.6 Echocardiography

Echocardiography evaluation is not a mandatory requirement of the protocol; in case the evaluation is performed and the values obtained are available in the source documents, they need to be entered into eCRF. Most recent data up to the last 12 months can be entered.

7 Safety monitoring

All AEs will be collected through Day 5, and all serious adverse events will be collected through Day 14, regardless of suspected causality. After Day 14 only suspected SAEs will be collected and databased.

Specific handling of the Study Endpoint WHF:

WHF events should be recorded not only as an endpoint but systematically as an AE as well. All WHF endpoints should thus be reported as AEs/SAEs in the AE eCRF page.

Non-serious WHF event should be reported through Day 5 and serious (SAE) WHFs should be reported through Day 14. After Day 14, only those study endpoints that qualify for SAEs and are also suspected to be related to the study medication should be reported in the AE eCRF page. It is recommended but not mandatory that the same verbatim should be used for an individual event for both the endpoint reporting and the AE reporting, i.e. "Worsening of Heart Failure".

